Effect of ATG16L1 allelic variation on neutrophil longevity. Autophagy 16-like 1 (ATG16L1) is an essential part of a protein complex responsible for initiating and carrying out autophagy. Autophagy is an essential intracellular process necessary for intracellular degradation and involves autophagosome and lysosome formation. Most people carry non-mutant, or “hypermorphic,” alleles for ATG16L1 allowing for the proper degradation of unneeded intracellular components. However, some carry mutant, or “hypomorphic,” alleles that disrupt normal autophagic processes. This disruption in proper autophagy leads to improper and excessive inflammatory responses by the innate immune system. Patients both heterozygous and homozygous for these hypomorphic alleles have a markedly increased risk of developing inflammatory bowel diseases, particularly Crohn’s disease. It has been shown that the presence of the hypomorphic ATG16L1 alleles also contribute to the development of ventilator associated pneumonia and other postoperative inflammatory complications³². However, the effect these alleles have on postoperative responses by the most prominent inflammatory immune cell the neutrophil, have yet to be elucidated. By isolation and subsequent sequencing of these alleles in neutrophils from patients with and without postoperative inflammatory complications, we can further understand how this gene plays a role in thoracic immune response.

Mitochondrial DNA released during cellular injury or trauma has been implicated in sterile inflammation. Injured cells release a variety of molecules capable of eliciting an innate immune response to non-bacterial products. The presence of mitochondrial DNA (mtDNA) released during cell injury has been implicated in development of non-bacterial or sterile inflammation by activation of human neutrophils leading to increased migration, activation and degranulation mediated by Ca^{2+} and mitogen-activated protein kinases (MAPK). Studies of trauma patients with evidence of systemic inflammation indicate that DAMPs are present in the serum of affected patients and in particular mtDNA has been detected at levels several times higher than patients without trauma. Less is known of local cellular injury and in particular in the tracheal area during active injury such as endotracheal tube presence. The mechanisms involved in PMN activation resulting in tracheal and airway injury have not been elucidated, hence our interest in studying mtDNA locally with the goal to determine its impact on PMN activation and thus design therapies directed to specific anti-inflammatory targets using anti-mitochondrial DNA³⁷.

Neutrophil are essential cells of the innate immune system and have multiple defensive functions intended to protect tissue homeostasis. As part of the extracellular neutrophil activity a release of a substance call neutrophil extracellular traps (NETs)³⁸ may occur and appears to have a phagocytic function. NETs are also regarded as a form of cell death different than apoptosis or necrosis. We are asking for approval to stain the neutrophil human cell to determine the level of NET formation under the conditions previously requested in the initial protocol. No extra specimens are requested.

Innovation:

CONFIDENTIAL: This document is the intellectual property of [name]. Acceptance of this document constitutes the agreement by the recipient that no unpublished information contained herein will be published or disclosed without prior written approval.

DoCTR

The use of endotracheal intubation as a procedure to facilitate general anesthesia and provide airway protection in the intensive care unit and may result in a variety of airway injuries including sore throat. There is no current therapy universally accepted for prevention of sore throat despite a multitude of pharmacological and non-pharmacological interventions. Tracheal research is in itself innovative and analysis of local PMN activation in the context of acute tracheal injury represents a new approach in the quest to understand the pathophysiology of sore throat. Patient satisfaction after surgery is negatively influenced in part by sore throat. Identification of specific PMN surface receptors will provide therapeutic targets that can be used to modulate the inflammatory reaction and facilitate healing. The primary aim of this research is to improve understanding of the cellular mechanisms involved in sore throat following endotracheal intubation. If neutrophil activation patterns are correlated with occurrence of sore throat, more precise treatment(s) and preventive measurements can be taken to improve quality of patient care, satisfaction, safety and outcomes. This study may provide sufficient evidence to support new treatments such as anti-IL-6, anti-TNF-alpha, Apyrase and other anti-inflammatory medications to coat the endotracheal tube and thus prevent sore throat and inflammation.

Healthy Volunteers

We found inflammation in the tracheal lavages of healthy humans indicating that neutrophil activation is occurring while the endotracheal tube is in place. We hypothesize that the inflammation is mainly mediated by sterile products in particular necrotic tissue or cellular mitochondrial DNA resulting from local cell injury. Now we would like to recreate similar neutrophil response by looking in the blood of healthy volunteers and challenge the neutrophils with necrotic tissue or labeled mitochondrial DNA obtained from laboratory cultured cells and look for markers of neutrophil activation that also will include CD35/CD49b, connexin43 and the previously approved CD markers. By exploring the role of CD35/CD49b39 and possibly connexin4340 we could attempt to understand how the neutrophil cell respond to exposure to necrotic tissue and what possible mechanisms are involved in the responses. Determination of NET's (neutrophil extracellular traps) will be also done as proposed previously for airway neutrophils. If recreation of the cellular injury in the blood neutrophil results in similar cellular changes as the ones seen in the trachea, then we will have a good human model to study airway inflammation.

Approach

2.1.1 Preliminary Data

[figure not shown]
2.2 Objective

The study is aimed at identifying neutrophil surface changes that occur during tracheal injury secondary to endotracheal intubation and to correlate them with the development of sore throat.

2.3 Patient Selection

CONFIDENTIAL: This document is the intellectual property of [name]. Acceptance of this document constitutes the agreement by the recipient that no unpublished information contained herein will be published or disclosed without prior written approval.

DoCTR

2.3.1 Inclusion Criteria

1. Ages 18 to 65
2. American Society of Anesthesiologists Physical Status Classification (ASA) I and II as determined by the study physician as this is a subjective measure.
3. Required to have endotracheal intubation
4. Scheduled for short admission (<23 hrs), or ambulatory orthopedic surgery (ankle, shoulder, or extremity surgery); general surgery (exploratory laparotomy, cholecystectomy, hernia repairs); obstetric/gynecological surgery (total abdominal hysterectomy, bilateral salpingo-Oophorectomy); urologic surgery (nephrectomy, prostatectomy), lumbar spine surgery (discectomy, one or two level lumbar fusion) procedures.
- 5.
6. Provide informed consent.

2.3.2 Exclusion Criteria

1. Active pulmonary disease within 5 days prior to enrollment
2. On immunosuppressive medications
3. Previous tracheal surgery
4. On azithromycin
5. Diabetes
6. Pregnancy
7. Smoking history of less than 6 weeks prior to surgery
8. Surgery or intubation within 5 days of surgery
9. Planned surgical procedure involving neck or thoracic regions
10. Active pulmonary disease
11. Autoimmune disease (HIV, AIDS, Rheumatoid Arthritis)
12. Hepatitis B or C, or active Hepatitis A
13. Cancer

Healthy Controls:

Inclusion:

1. Ages 18 to 65
2. Provide informed consent

2.4 Design and Procedures

[figure not shown]
2.4.1 Study Design

This study is observational and prospective.

2.4.2 Minimization of Bias

CONFIDENTIAL: This document is the intellectual property of [name]. Acceptance of this document constitutes the agreement by the recipient that no unpublished information contained herein will be published or disclosed without prior written approval.

DoCTR

There will be no specific gender or ethnic background for enrollment and the decision to place the endotracheal tube will be at the discretion of the attending anesthesiologist. Addition of CD35/CD49b and connexin43 will be done to determine neutrophil activity and subpopulation of neutrophils active during different conditions and may result in local inflammation or immune-suppression.

2.4.3 Pre-Study Period

Subjects who are potential candidates for the study will be educated as to the study procedures, benefits, and potential risks. Each subject who qualifies for entry into the study on the basis of inclusion/exclusion criteria, and completion of an informed consent will be assigned the next available patient number. This indicates enrollment in the study. Subjects who drop out of the study prior to completing the study will be replaced by using the next available patient number.

2.4.4 Study Period

Subjects will participate from intubation time to the immediate post operative period.

After the placement of the endotracheal tube (Hi-Lo™ Evac Mallinckrodt), tracheal lavages will be performed using 5 milliliters of sterile saline solution by a push/suction technique. Wall suction will be set to a minimum in order to minimize tracheal injury and to comply with standards of medical care. The same procedure for collection of tracheal sample will be repeated at the end of the surgical procedure, immediately prior to removal of the ETT. The specimen will be collected in a sterile container and placed in a laden ice container for transportation and immediate processing.

A simultaneous blood sample of approx 5cc, will be collected by venipuncture or by sampling from intravenous or arterial line if available at the end of the surgical procedure, immediately prior to removal of the ETT. A total of approx 5cc blood will be collected for research purposes.

Review of the medical record will be conducted for data acquisition of medical history, and preoperative blood test results to determine enrollment in the study according to the specified inclusion or exclusion criteria protocol. Physiologic and demographic measurements such as temperature, oxygenation, and blood pressure, gender, body mass index and coexisting diseases will be recorded as per anesthesia records. All data will be de- identified. All patients will be asked to respond to presence or absence of sore throat and its degree of intensity using a Visual Analogue Scale (VAS) sliding scale at 120 minutes post extubation and following a specific cognitive assessment performed by the recovery room nurses as part of their discharge protocol. Cognitive evaluation will include patient interview to determine the following: Orientation to time, place, person and situational (Why are you here?).

Healthy volunteers

A blood sample of approx 20cc, will be collected by venipuncture for research purposes to challenge the neutrophils with necrotic tissue obtained from laboratory cultured cells and look for markers of neutrophil activation that also will include CD35/CD49b and the previously approved CD markers

CONFIDENTIAL: This document is the intellectual property of [name]. Acceptance of this document constitutes the agreement by the recipient that no unpublished information contained herein will be published or disclosed without prior written approval.

DoCTR

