1. SYNOPSIS

Study Title	Sore throat secondary to endotracheal intubation: the role of neutrophil activation
Objective	The study is aimed at identifying neutrophil surface changes that occur during tracheal injury secondary to endotracheal intubation and to correlate them with the development of sore throat.
Study Period	Planned enrollment duration: 1 year Planned study duration: Subjects will participate from time of consent prior to surgery through approximately 120 minutes following extubation.
Number of Patients	60 evaluable patients and 25 evaluable healthy controls
Study Treatment	Patients will undergo placement of an endotracheal tube (ETT) as standard of care. Tracheal lavage will be conducted using 5 mL of sterile saline solution by a push/suction technique. Specimen samples obtained by wall suction will be collected at 2 time points following intubation. Blood samples will be obtained at 2 time points, simultaneous with the collection of the tracheal specimens. Healthy volunteers will have a blood draw.
Study Design	This study is prospective.
Inclusion and Exclusion Criteria	Inclusion: 1. Ages 18 to 65 2. American Society of Anesthesiologists Physical Status Classification (ASA) I and II as determined by the study physician as this is a subjective measure. 3. Required to have endotracheal intubation 4. Scheduled for short admission (<23 hrs), or ambulatory orthopedic surgery (ankle, shoulder, or extremity surgery); general surgery (exploratory laparotomy, cholecystectomy, ventral or inguinal hernia repair); obstetric/gynecological surgery (total abdominal hysterectomy, bilateral salpingo-oophorectomy); urologic surgery (nephrectomy, prostatectomy), lumbar spine surgery (discectomy, one or two level lumbar fusion) procedures

CONFIDENTIAL: This document is the intellectual property of [name]. Acceptance of this document constitutes the agreement by the recipient that no unpublished information contained herein will be published or disclosed without prior written approval.

DoCTR

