	
cytokines (R&D Systems, Minneapolis, MN).
 
Toll-like Receptors (TLR) Determination of TLR-2, TLR-4 and TLR-9 and Mitochondrial DNA will be done by PCR.
 
Neutrophil extracellular traps (NETs) formation Neutrophil cells will be stained and photographic documentation of the NET presence will be documented.

Statistical Methodology
	
The primary aim of this study is to describe the inflammatory changes that result in a neutrophil surface receptor expression unique to the interaction between the trachea and ETT resulting in sore throat. Blood samples will be obtained and neutrophil cells (PMN) will be isolated for analysis at the same time intervals as the tracheal lavage samples. Individual indicators of inflammation (PMN, cytokines, clusters of differentiation –CD, TLR's as described above) will be compared to baseline values of these variables measured at time zero. We will compare neutrophil (PMN) changes between patients who developed sore throat and those who do not by using the Wilcoxon rank sum test, since we expect the data to be non-normally distributed. With a sample size of 60 patients, we will have at least 80% power to detect large differences (Cohen's $D \geq 0.8$) between the sore throat and non-sore throat groups with an alpha level of 0.05 and assuming that half of the participants report a sore throat following intubation. As our pilot study is exploratory, we did not inflate our sample size to account for multiple testing. We will confirm any identified associations found in our pilot study with a future larger study. Subjects who undergo intubation attempts $\times 2$ or greater will be considered a subset population and not part of the 60 evaluable patients. Assuming that lack of sore throat relates to anti-inflammation, measuring a biomarker such as IL-10, may provide information on the regulatory function of this cytokine. We have observed that IL-10 at a concentration of 200 pg/ml generated by PMNs inhibited reactive oxygen species burst from alveolar macrophages challenged by LPS. Power analysis was conducted for two tailed T-test using the following assumptions: a standard deviation of 100 pg/ml. A difference of 75 pg/ml between the two groups will be considered a significant difference. We will need approximately 30 patients per group for an alpha 0.05 and Beta of 0.2.

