Several systemic diseases and certain antibiotics may alter PMN responsiveness to injury. A variety of systemic diseases such as diabetes, rheumatoid arthritis, acute lung injury and several others may affect local PMN responses to injury by altering inflammation, apoptosis and proper anti-inflammation. In the case of diabetes with microangiopathy surface receptor CD11b was elevated and CD62L was decreased²⁷. The impact of macrolide antibiotics and in particular azithromycin in the improved outcome of respiratory diseases such as acute lung injury (ALI), community-acquired pneumonia (CAP) and ventilator associated pneumonia (VAP) appear to be mediated by its anti-inflammatory properties. In particular azithromycin may affect PMN activation, PMN survival, oxidative burst, and attenuation of nuclear factor- κB ²⁸, therefore modulating the inflammatory response. It is not known the exact effect of these systemic factors in the local expression of neutrophils at the tracheal level, therefore our interest to compare local and systemic PMN activation in the healthy subject.

CONFIDENTIAL: This document is the intellectual property of [name]. Acceptance of this document constitutes the agreement by the recipient that no unpublished information contained herein will be published or disclosed without prior written approval.

DoCTR

A variety of biomaterials activate PMN in blood. The endotracheal tubes contain a biomaterial known as di-(2-ethyl-hexyl)-phthalate or DEHP as it is commonly known. Studies in human and rat blood have shown its ability to increased CD-11b expression in PMN cells²⁹. The effects on PMN of neonates also include inhibition of chemotaxis, stimulation of oxidative metabolism, and upregulation of NADPH-oxidase-1³⁰. DEHP is the only plasticizer approved for human devices by the U.S. Food and Drug Administration. Studies of materials involved either human blood samples, or *in vitro*, or rat models, none have *in vivo* local activation of PMN cells.

Significance of intubation related sore-throat in airway inflammation VAT/VAP:

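### Section 2.4.4 schedules one patient blood draw, at the end of surgery, while the synopsis and 2.5.9 call for blood at both lavage times; if 2.4.4 is followed, no patient has a time-zero blood value

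*Combined protocol and SAP*

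**What the plan says.** **Collection instructions (section 2.4.4).** Two tracheal lavages are scheduled. The first follows placement of the tube. The text on the second reads "The same procedure for collection of tracheal sample will be repeated at the end of the surgical procedure, immediately prior to removal of the ETT", which fixes its time. Patient blood is described in the singular, as one sample of about 5 cc. Apart from venipuncture, the stated route and time are "by sampling from intravenous or arterial line if available at the end of the surgical procedure, immediately prior to removal of the ETT", with no earlier draw mentioned. The volume is then closed off: "A total of approx 5cc blood will be collected for research purposes".

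**Synopsis, Study Treatment.** For the lavages: "Specimen samples obtained by wall suction will be collected at 2 time points following intubation". For blood: "Blood samples will be obtained at 2 time points, simultaneous with the collection of the tracheal specimens".

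**Synopsis, Statistical Methodology, repeated in section 2.5.9.** On blood timing, the text reads "Blood samples will be obtained and neutrophil cells (PMN) will be isolated for analysis at the same time intervals as the tracheal lavage samples", and on the baseline it says that the markers of inflammation "will be compared to baseline values of these variables measured at time zero". Changes in neutrophils are then compared between patients with and without sore throat by the Wilcoxon rank sum test. Neither section defines time zero.

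**Background (section 2.1).** Blood is wanted for a comparison of the two compartments: "therefore our interest to compare local and systemic PMN activation in the healthy subject".

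**The concern.** The section that directs sample collection gives one blood draw. The synopsis and the statistical section assume two. A coordinator working from 2.4.4 would draw blood only before the tube is removed, and a first sample that was not drawn cannot be recovered later.

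Without that first sample, change in blood markers cannot be calculated for any patient. A difference in end-of-surgery blood values between the sore-throat and no-sore-throat groups could not then be separated from a difference that was already present at the start. If some staff followed 2.4.4 and others the synopsis, some patients would have pairs and others would not, for reasons unrelated to the design.

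The stated research blood volume is also in question, because it fits only one of the two schedules.

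**Working it through.** **Inputs**
- Evaluable patients: 60 (synopsis; section 2.5.10).
- Lavages per patient: 2 (synopsis; section 2.4.4).
- Blood samples per patient: 2 in the synopsis (Study Treatment), 1 in section 2.4.4.
- Volume per patient blood sample: about 5 cc (section 2.4.4).
- Total research blood per patient: about 5 cc (section 2.4.4).

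**1. Reproduce the stated volume.** Draws × volume per draw = 1 × 5 cc = 5 cc. This equals the total in 2.4.4, so that section is consistent with itself on one draw.

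**2. Apply the synopsis schedule.** 2 × 5 cc = 10 cc, twice the stated total. Two draws fit within 5 cc only if each is about half the stated sample size, and no section says so.

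**3. Count specimens.**

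| | Synopsis | Section 2.4.4 | Not collected under 2.4.4 |
|---|---|---|---|
| Lavage | 60 × 2 = 120 | 60 × 2 = 120 | 0 |
| Blood | 60 × 2 = 120 | 60 × 1 = 60 | 60 (60/120 = 50%) |
| Patients with paired blood | 60 of 60 | 0 of 60 | all |

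**4. Look for another source of a time-zero blood value.**
- The preoperative blood tests in 2.4.4 are chart results used to judge eligibility. They are not research measurements of neutrophil markers.
- The healthy-volunteer sample of about 20 cc comes from other people and is not a within-patient baseline.

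Neither supplies the missing value.

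**5. Check the reach.**
- Lavage keeps both samples, so change in the trachea can still be computed.
- The interest in local versus systemic neutrophils in section 2.1 concerns activation, not change. It can be met with the paired end-of-surgery samples.
- The power statement in 2.5.10 does not depend on the number of draws. With 30 against 30 patients, a standardised difference of 0.8 and alpha 0.05 (two-sided assumed), t-test power is 86.1%. For the Wilcoxon test it is about 84.5% at a relative efficiency of 0.955 and 80.6% at the worst-case 0.864. The claim of at least 80% reproduces.

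**The case against.** The strongest reply concedes that the texts conflict but disputes how much is lost.

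- **Compartment not named.** The sentences on comparison with time zero and on neutrophil changes do not say blood. Lavage alone, with two samples, could satisfy them literally. This has some force: the blood-change analysis is a reading of the text. It is the natural reading, because the sentence just before concerns blood taken at the lavage times, and taking blood at those times serves little purpose if change in blood is not examined.
- **Exploratory, airway-focused study.** The objective concerns tracheal injury, and findings are to be confirmed in a larger study. That limits the consequence to one systemic analysis. It does not reconcile the sections or recover an undrawn sample.
- **Ambiguous timing.** The clause on end of surgery might qualify only whether a line is available. The single sample and the 5 cc total would still allow only one draw of the stated size.
- **Unseen material.** A figure under section 2.4 is not shown and may hold a schedule. It could show which version was meant, but the written sections would still disagree.
- **Timing and cost of the repair.** The protocol mentions previously approved markers and specimens already collected, so sampling may have begun. Taking two draws of the stated size also means doubling the stated volume. Both points stand and bear on the fix, not on whether the contradiction exists.

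**Conclusion.** The concern holds. Section 2.4.4 provides one patient blood sample; the synopsis and 2.5.9 require two. If 2.4.4 governs, 60 of 120 blood specimens (50%) are not collected and 0 of 60 patients have a baseline blood value, so the blood change analysis is lost entirely and irrecoverably. If the synopsis governs, the stated blood total is half of what two samples of the stated size require.

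This rests on two assumptions: that staff follow 2.4.4 as written, and that the indicators to be compared with time zero include those measured in blood. The damage is confined to change in blood. Lavage change, the end-of-surgery comparison of trachea and blood, and the power statement stand. The point must still be fixed, because the loss cannot be repaired after the operation and the correction is simple.

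**What to change.** Reconcile the synopsis (Study Treatment and Statistical Methodology), section 2.4.4 and section 2.5.9 before any further patient is sampled. There are two consistent versions.

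**(a) Keep two draws.** State in 2.4.4 that blood is taken with each lavage, correct the total research blood volume (about 10 cc if each sample stays at about 5 cc), and define time zero as the first paired lavage and blood sample. Say plainly that this baseline is taken after intubation and is not a pre-exposure value. Bring the risk text in 3.3.2, which speaks of a single blood sample, into line. This version supports change from time zero in blood.

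**(b) Keep one draw.** Remove the two-time-point and same-interval wording for blood, define time zero as the first lavage, exclude blood from the change analysis, and limit blood to end-of-surgery comparisons.

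If patients have already been sampled, record which draws each one had and report that with the results.

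**Cost.** Both are protocol amendments. Version (a) adds no sample beyond what the synopsis already promises, and 3.3.2 already plans to use an indwelling catheter where possible, but the larger stated volume must be carried through the study documents. Version (b) adds no procedure and gives up the blood change analysis.

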2.5.9 Statistical Methods

CONFIDENTIAL: This document is the intellectual property of [name]. Acceptance of this document constitutes the agreement by the recipient that no unpublished information contained herein will be published or disclosed without prior written approval.

DoCTR

The primary aim of this study is to describe the inflammatory changes that result in a neutrophil surface receptor expression unique to the interaction between the trachea and the ETT and result in sore throat. Blood samples will be obtained and neutrophil cells (PMN) will be isolated for analysis at the same time intervals as the tracheal lavage samples. Individual indicators of inflammation (PMN, cytokines, clusters of differentiation –CD, TLR's as described above) will be collected at specific pre-determined times and will be compared to baseline values of these variables measured at time zero. We will compare neutrophil (PMN) changes between patients who developed sore throat and those who do not by using the Wilcoxon rank sum test, since we expect the data to be non-normally distributed.

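### Sore throat is asked about only at 120 minutes after extubation, so a sore throat present before surgery is analysed as one that developed after intubation

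*Combined protocol and SAP*

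**What the plan says.** The objective (2.2) is to identify neutrophil surface changes and "to correlate them with the development of sore throat"; 2.5.7 repeats this as the primary outcome. The analysis (2.5.9) states: "We will compare neutrophil (PMN) changes between patients who developed sore throat and those who do not". Grouping is thus by onset.

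The symptom is measured once. Section 2.4.4 says "All patients will be asked to respond to presence or absence of sore throat and its degree of intensity". The single occasion is 120 minutes after extubation, with intensity scored on a VAS. Section 4.2 repeats presence or absence and severity and adds no other time. The question is not restricted to new symptoms.

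For the period before surgery, 2.4.4 offers the record: "Review of the medical record will be conducted for data acquisition of medical history, and preoperative blood test results". It also lists physiologic and demographic measurements and coexisting diseases. No throat symptom is among them. The same section opens with "Subjects will participate from intubation time to the immediate post operative period", although the synopsis starts participation at consent.

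The nearest exclusions in 2.3.2 are "Active pulmonary disease within 5 days prior to enrollment" and "Surgery or intubation within 5 days of surgery". Pharyngitis, a cold and a current sore throat are not named there or in the synopsis.

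**The concern.** A symptom can be said to have developed only if it was absent before, and absence before is never recorded. Followed exactly, the plan puts a patient with a pre-existing sore throat that persists to 120 minutes into the sore-throat group. The gap cannot be closed afterwards: the record need not mention a mild sore throat, and the assays in 2.5.1 to 2.5.6 include no microbiology that would show an infection.

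This matters for the hypothesis. Section 2.1 proposes that the inflammation is mainly a sterile response to tube injury, and also says that neutrophils respond to bacterial as well as sterile stimuli. A sore throat that came in with the patient bears on neither the tube nor sterile injury. The protocol already excludes diabetes, rheumatoid arthritis and azithromycin, which 2.1 says may alter neutrophil responses. An upper-airway infection lies closer to the sampled site and is not addressed.

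**Working it through.** **1. The plan's own figure.** Inputs from 2.5.10: 60 evaluable patients, half with sore throat (30 v 30), d = 0.8, alpha 0.05 (taken as two-sided), power 80% or more.

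- Normal approximation: Φ(0.8 × √(30/2) − 1.96) = Φ(1.138) = 87.3%.
- t-test: 86.1%.
- Wilcoxon with efficiency 3/π (30 × 0.955 = 28.6 effective per group): 84.5%. By simulation with normal data, 20,000 runs: 83.9%.

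The stated figure reproduces. The issue is the outcome definition, not the arithmetic.

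**2. Dilution.** Assume that k of the 30 patients labelled as sore throat had only a pre-existing sore throat and have the marker distribution of the other group. The mean difference becomes 0.8 × (1 − k/30). Simulated Wilcoxon power (20,000 runs per row):

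| k of 30 | Mean difference (SD) | Power |
|---|---|---|
| 0 | 0.80 | 83.9% |
| 1 | 0.77 | 81.6% |
| 2 | 0.75 | 78.3% |
| 3 | 0.72 | 75.0% |
| 6 | 0.64 | 64.3% |

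Two mislabelled patients are enough to fall below 80%.

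**3. From prevalence to k.** The documents give no prevalence, so take 5% and 10% as assumed values. Suppose every patient who arrives with a sore throat still reports it, and half of them would have had one from the tube anyway.

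- 5%: 60 × 0.05 × 0.5 = 1.5 mislabelled among 31.5 labelled cases; difference 0.76 SD; t-test power 82.6%.
- 10%: 60 × 0.10 × 0.5 = 3 mislabelled among 33; difference 0.73 SD; t-test power 78.7%.

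The undiluted t-test value is 86.1%. Wilcoxon power would be somewhat lower throughout.

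**4. Spurious association.** Now assume no true effect, with m of the 30 labelled cases shifted by s SD in the value analysed. The mean bias is (m/30) × s. Simulated rejection rates of a two-sided Wilcoxon test at 0.05:

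| m | s = 1 | s = 1.5 | s = 2 | s = 0.25 to 0.5 |
|---|---|---|---|---|
| 3 | 6.0% | 6.6% | 7.3% | 4.7 to 5.1% |
| 6 | 9.0% | 13.2% | 17.0% | 5.0 to 5.9% |

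(4,000 runs for s = 1 to 2; 8,000 for the last column, where the simulation standard error at 5% is √(0.05 × 0.95/8000) = 0.24 percentage points.)

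The value analysed is a change from time zero (2.5.9), so s is the net shift in the change. A stable elevation present in both lavages cancels. The last column shows the case where a quarter of a 1 to 2 SD elevation survives, which is an assumption.

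**The case against.** The strongest reply is that the plan compares changes. The first lavage follows tube placement and the second precedes extubation, so inflammation present on arrival raises both and largely drops out. This stands for the marker values, most clearly for lavage. For blood it is less sure: 2.4.4 describes a sample only at the end of surgery, while the synopsis has two. It does not repair the group label, because the baseline is for markers only.

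Second, a reader might infer that every symptomatic patient lands in the sore-throat group and that the design manufactures the association it seeks, with error rates of 9 to 17%. The documents do not support this. A patient with a recent cold may have no throat pain and answer no, and a mild sore throat may not be reported at 120 minutes. With an incidence near 50% (2.1), about half of those who arrive with one might have had a sore throat from the tube anyway. The 9 to 17% requires six affected patients, all in one group, with the full 1 to 2 SD surviving in the change score. An already inflamed airway might also rise less, which would bias against the association.

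Third, there are partial safeguards: ASA I or II, exclusion of active pulmonary disease and recent intubation, record review and recorded temperature. They lower the risk, but none is a throat-symptom screen. If the site reads pulmonary disease to include colds, the text should say so.

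Finally, this is an exploratory pilot. That limits the consequence, but 2.5.10 intends to carry associations into a larger study, which could inherit the same definition.

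**Conclusion.** The point holds as a defect in outcome definition. The plan analyses sore throat that developed but records only sore throat that is present, and no planned item separates the two. That conclusion rests on the text alone.

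The size rests on assumptions. Under dilution, two mislabelled patients among 30 take Wilcoxon power from about 84% to 78%, three to 75% and six to 64%. How many there would be is unknown. The false-positive risk is secondary: close to the nominal 5% unless several patients have a large net shift in the change score. The direction of bias is not settled by the documents. The matter merits correction because the remedy is cheap and cannot be applied after data collection.

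**What to change.** - **2.4.4:** ask the same presence-or-absence and VAS sore-throat question before surgery, at consent in the holding area (4.3), and record any current upper respiratory symptoms. Align the start of participation with the synopsis.
- **2.5.7, 2.5.9 and the synopsis:** define the outcome as sore throat present at 120 minutes and absent before surgery.
- **2.5.10:** treat patients with a pre-operative sore throat as not evaluable for the primary comparison and replace them. The section already makes patients with two or more intubation attempts non-evaluable.
- **2.5.9:** add a sensitivity analysis that omits patients with current upper respiratory symptoms but no sore throat. The documents give no basis for a fixed look-back window, so current symptoms suffice.

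The cost is one or two questions, with the VAS ruler already in use (4.2), a short amendment and a few replacements. At an assumed 5 to 10% prevalence, 60 evaluable patients need about 60/0.95 = 63 to 60/0.90 = 67 enrolled, before other losses.
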